5.9.2. Anti-Diarrheal, Anti-Emetic Therapy

Primary prophylaxis of diarrhea, nausea and vomiting is not permitted in the first cycle. Primary prophylaxis in subsequent cycles is at the investigator's discretion. The choice of the prophylactic drug as well as the duration of treatment is up to the investigator with sponsor approval assuming there is no known or expected DDI and assuming the drug is not included in the Concomitant Treatment(s) section.

5.9.3. Anti-Inflammatory Therapy

Anti-inflammatory or narcotic analgesic may be offered as needed assuming there is no known or expected DDI and assuming the drug is not included in the Concomitant Treatment(s) section.

5.9.4. Corticosteroids

Chronic systemic corticosteroid use (prednisone >15 mg/day or equivalents) for palliative or supportive purposes is permitted. However, corticosteroids use for a short duration (eg, ≤15 mg/day of prednisone, for 2 weeks) as symptomatic treatment on individual basis may be considered after discussion with sponsor's medical monitor or designee. Acute emergency administration, topical applications, inhaled sprays, eye drops, or local injections of corticosteroids are allowed.

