5.7. Concomitant Treatment(s)

Concomitant treatment considered necessary for the patient's well-being may be given at discretion of the treating physician (including bisphosphonates or approved RANK ligand (RANK-L) targeted agents (for example, denosumab).

All concomitant treatments, blood products, as well as nondrug interventions received by patients from screening until the end of study visit will be recorded on the CRF.

Anticoagulation therapy with heparin, low molecular weight heparin, vitamin K antagonists, anti platelet agents, or factor Xa inhibitors is prohibited throughout the study and for at least 28 days post the last dose of study treatment. If anticoagulation therapy is medically indicated on trial, patients should stop treatment with PF-06952229. For those requiring temporary anticoagulant therapy, resumption of PF-06952229 treatment may be permitted after discussion with the Sponsor. In any other case, study treatment should be permanently discontinued, and the patient should enter the follow-up portion of the trial.

Because inhibition of CYP3A4/5 isoenzymes may increase PF-06952229 exposure leading to potential increases in toxicities, the use of known strong and moderate inhibitors are not permitted within 10 days or 5 half-lives of the CYP3A4/5 inhibitors, whichever is longer prior to the first dose of PF-06952229. A list of CYP3A4/5 inhibitors is provided in Appendix 9.

Because induction of CYP3A4/5 isoenzymes may decrease PF-06952229 exposure leading to potential decrease in efficacy, the use of strong or moderate CYP3A4/5 inducers is not permitted within 10 days or 5 half-lives of CYP3A4/5 inducers, whichever is longer prior to the first dose of PF-06952229. A list of CYP3A4/5 inducers is provided in Appendix 9.

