5.9. Supportive Care

Palliative and supportive care for disease related symptoms may be administered at the investigator's discretion and according to any available American Society of Clinical Oncology (ASCO) guidelines.

Patients currently being treated with a gonadotropin-releasing hormone agonist (GnRH agonist) may continue treatment while on clinical study C3881001 as long as the GnRH agonist treatment has been well tolerated for at least 3 months prior to study entry. If patients have had tolerability issues with GnRH agonists, such patients may be allowed to enroll with agreement of the Pfizer medical monitor.

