5.9.1. Hematopoietic Growth Factors

Primary prophylactic use of granulocyte-colony stimulating factors is not permitted during the first 14 days of Cycle 1, but they may be used to treat treatment emergent neutropenia as

indicated by the current American Society of Clinical Oncology guidelines or the relevant full prescribing information for the growth factor.

Erythropoietin or other erythropoiesis stimulating agents (ESAs) may be used at the investigator's discretion for the supportive treatment of anemia as described in current American Society of Clinical Oncology/American Society of Hematology guidelines or the relevant full prescribing information.

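### Protocol 5.9.4 puts its steroid control on the smaller exposure: chronic prednisone above 15 mg/day needs no sponsor step, while a short course at or below 15 mg/day needs a medical-monitor discussion

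*Protocol*

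**What the plan says.** Protocol Section 5.9.4 has three sentences.

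- The first covers long-term use: "Chronic systemic corticosteroid use (prednisone >15 mg/day or equivalents) for palliative or supportive purposes is permitted". It sets no condition on approval, notification or duration.
- The second opens with 'However' and covers short use, with prednisone at or below 15 mg/day for 2 weeks as its example. Such use, "as symptomatic treatment on individual basis may be considered after discussion with sponsor's medical monitor or designee".
- The third allows emergency, topical, inhaled, ocular and locally injected steroids without condition.

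The surrounding text is general. Section 5.9 says: "Palliative and supportive care for disease related symptoms may be administered at the investigator's discretion". Section 5.7 says: "Concomitant treatment considered necessary for the patient's well-being may be given at discretion of the treating physician". Section 5.9.3 says: "Anti-inflammatory or narcotic analgesic may be offered as needed assuming there is no known or expected DDI". None of the three names corticosteroids. Section 5.7 also requires that concomitant treatments "received by patients from screening until the end of study visit will be recorded on the CRF".

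**The concern.** A rule on concomitant steroids would normally put the tighter control on the higher dose and longer duration. Here it is the other way round. A site that follows the text literally may start chronic prednisone above 15 mg/day without contacting the sponsor, yet must call before giving two weeks at or below 15 mg/day. A site that guesses the intended rule may do something different.

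This is an operative treatment instruction in a multi-center study. At stake are consistent practice between sites and whether the sponsor hears about the larger steroid exposure before it starts.

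**Working it through.** There is no figure to reproduce. The check sets the sentences of 5.9.4 side by side, tests the two drafting errors that could explain them, and looks for a correcting rule elsewhere.

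**Step 1. What each reading gives.** Doses are prednisone or equivalent.

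| Exposure | As printed | If 'not' was omitted from sentence 1 | If the two dose signs were transposed |
|---|---|---|---|
| Chronic, above 15 mg/day | Permitted, no sponsor step | Prohibited | No specific rule; could fall back on 5.7 and 5.9 |
| Chronic, at or below 15 mg/day | No specific rule in 5.9.4; general rules in 5.7 and 5.9 apply | Same as printed | Permitted, no sponsor step |
| Short, at or below 15 mg/day | Medical-monitor discussion | Medical-monitor discussion | Covered by sentence 2 only if its example is read as open-ended |
| Short, above 15 mg/day, not an emergency | Covered by sentence 2 only if its example is read as open-ended | Same as printed | Medical-monitor discussion |
| Emergency, topical, inhaled, ocular, local | Allowed | Allowed | Allowed |

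The first and third rows of the 'as printed' column show the inversion: the larger exposure carries no sponsor step and the smaller one carries a sponsor step.

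**Step 2. Evidence on the cause.**

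- *Omitted 'not'.* 'However' followed by a limited allowance makes sense after a prohibition and does little work after a broader permission. The third sentence also reads most naturally as a list of exceptions to a restriction. Neighbouring sections follow the same pattern. Section 5.9.1: "Primary prophylactic use of granulocyte-colony stimulating factors is not permitted during the first 14 days of Cycle 1, but they may be used". Section 5.9.2: "Primary prophylaxis of diarrhea, nausea and vomiting is not permitted in the first cycle", after which later cycles are left to the investigator. Those two sections concern primary prophylaxis, so the parallel is suggestive and not conclusive.
- *Transposed signs.* Chronic low-dose use would be permitted and a short higher-dose course would need a call. 'However' then also reads naturally, and a permissive first sentence agrees with 5.7, 5.9 and 5.9.3.

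The omitted 'not' is the more plausible of the two. That is an inference, because the documents do not show the intended wording.

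**Step 3. Is it corrected elsewhere?** The eligibility criteria (4.1, 4.2) contain no steroid criterion. Sections 5.7, 5.8, 5.9 and 5.9.1 to 5.9.3 set no systemic steroid rule. Appendix 9 lists CYP3A4/5 inhibitors and inducers and names no corticosteroid. The SAP does not mention steroids. The discretion rules in 5.7 and 5.9 are compatible with the literal permission, so they give a site no ground to infer a limit.

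**The case against.** The strongest reply is that nothing here is contradictory. The two sentences can both be obeyed, and they describe different purposes: long-term palliative or supportive use, and short symptomatic treatment decided patient by patient. A permissive first sentence agrees with the discretion given in 5.7 and 5.9. There is also oversight: the sponsor gives written permission before a patient is dosed (5.1), safety is discussed regularly between investigators and sponsor (9.7), and concomitant treatment is recorded on the CRF (5.7).

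Much of this stands. The sentences are not in strict conflict. Chronic use at or below 15 mg/day is not without any rule, since the general discretion provisions reach it. If the signs were transposed, chronic use above 15 mg/day could still be left to the physician under those same provisions, so it cannot be said that every plausible repair puts that use under control.

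The reply does not explain why the lesser exposure should need a call when the greater does not, and the protocol gives no rationale for that. The oversight it cites is general: permission to dose comes before treatment, safety meetings do not name steroids, and CRF entry records use without controlling it.

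A reader might also infer that steroid use could distort the paired-biopsy T-cell endpoint in Part 2. That depends on steroids changing intra-tumor T-cell levels, which the documents do not say, so the point does not rest on it.

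**Conclusion.** The concern holds as a defect in a treatment rule: Section 5.9.4 as printed places its only sponsor step on the smaller systemic exposure, and no other text in the protocol or SAP corrects this. A drafting error is the likely explanation.

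No trial effect can be sized, because the documents do not report how many patients take systemic steroids, at what dose or for how long. No effect is shown on a primary endpoint, a dose-escalation decision or any statistical figure. The consequence that can be supported is narrower: literal compliance gives an inverted safeguard, and sites may differ in how they apply the rule.

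A reader might go further and conclude that chronic use above 15 mg/day was certainly meant to be banned. The text makes that the more plausible intent but does not establish it. The conclusion assumes that the redacted and removed parts of the public documents contain no steroid rule.

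**What to change.** The sponsor should confirm the intended rule and amend Section 5.9.4 accordingly. The wording depends on the answer; one text does not serve both cases.

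- *If a 'not' was omitted:* insert it, so that sentence 1 prohibits chronic systemic use above 15 mg/day for palliative or supportive purposes. Keep the short-course allowance and the emergency, topical, inhaled, ocular and local allowances as they are.
- *If the dose signs were transposed:* swap them, and add a sentence requiring prior discussion with the medical monitor for any non-emergency systemic use above 15 mg/day. Without that sentence, chronic use above the threshold could fall back on general discretion.

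The cost is one or two sentences in an amendment. Afterwards there would be occasional medical-monitor calls or, under the first option, a tighter limit on supportive steroids for some patients. Visits, sample size and analyses do not change.

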5.9.5. Surgery

Caution is advised on theoretical grounds for any surgical procedures during the study. The appropriate interval of time between surgery and PF-06952229 required to minimize the risk of impaired wound healing and bleeding has not been determined. Stopping PF-06952229 is recommended at least 14 days prior to surgery. Postoperatively, the decision to reinitiate PF-06952229 treatment should be based on a clinical assessment of satisfactory wound healing and recovery from surgery.

6. STUDY PROCEDURES

6.1. Screening

For screening procedures see the Schedule of Activities and Assessments sections.

6.2. Study Period

For the treatment period procedures, see the Schedule of Activities and Assessments sections.

6.3. Follow-up

For follow-up procedures see the Schedule of Activities and Assessments sections.

6.4. Patient Withdrawal

Withdrawal of Consent:

Patients who request to discontinue receipt of study treatment will remain in the study and must continue to be followed for protocol specified follow-up procedures. The only exception to this is when a patient specifically withdraws consent for any further contact with him or her or persons previously authorized by the patient to provide this information. Patients should notify the investigator in writing of the decision to withdraw consent from future follow-up, whenever possible. The withdrawal of consent should be explained in detail in the medical records by the investigator, as to whether the withdrawal is only from further receipt of investigational product or also from study procedures and/or posttreatment study follow-up, and entered on the appropriate CRF page. In the event that vital status (whether the patient is alive or dead) is being measured, publicly available information should be used to determine vital status only as appropriately directed in accordance with local law.

Lost to Follow-Up:

All reasonable efforts must be made to locate patients to determine and report their ongoing status. This includes follow-up with persons authorized by the patient as noted above. Lost to follow-up is defined by the inability to reach the patient after a minimum of 2 documented phone calls, faxes, or e-mails as well as lack of response by the patient to 1 registered mail letter. All attempts should be documented in the patient's medical records. If it is determined that the patient has died, the site will use locally permissible methods to obtain the date and cause of death. If the investigator's use of a third-party representative to assist in the follow-up portion of the study has been included in the patient's informed consent, then the investigator may use a sponsor-retained third-party representative to assist site staff with obtaining the patient's contact information or other public vital status data necessary to complete the follow-up portion of the study. The site staff and representative will consult publicly available sources, such as public health registries and databases, in order to obtain updated contact information. If, after all attempts, the patient remains lost to follow-up, then the last-known-alive date as determined by the investigator should be reported and documented in the patient's medical records.

Patients may withdraw from treatment at any time at their own request, or they may be withdrawn at any time at the discretion of the investigator or sponsor for safety (Withdrawal from the Study Due to Adverse Events (see also the Patient Withdrawal Section) or behavioral reasons, or the inability of the patient to comply with the protocol-required schedule of study visits or procedures at a given investigator site.

Patient may permanently discontinue study treatment (definitive discontinuation). Reasons for definitive discontinuation of study treatment may include the following:

- Objective disease progression;
- Global deterioration of health status requiring discontinuation;
- Unacceptable toxicity;
- Pregnancy;
- Significant protocol violation;
- Lost to follow-up;
- Patient refused further treatment;
- Study terminated by sponsor;
- Death.

Note that discontinuation of study treatment does not represent withdrawal from the study. If study treatment is definitively discontinued, the patient will remain in the study to be evaluated for AEs. See the Schedule of Activities for data to be collected at the time of discontinuation of study treatment and follow-up for any further evaluations that need to be completed.

In the event of discontinuation of study treatment, it must be documented on the appropriate CRF/in the medical records whether the patient is discontinuing further receipt of study treatment or also from study procedures, posttreatment study follow-up, and/or future collection of additional information.

A patient may withdraw from the study at any time at his/her own request. Reasons for discontinuation from the study may include:

- Completed study follow-up;
- Study terminated by sponsor;
- Lost to follow-up;
- Refused further follow-up;
- Death.

At the time of discontinuing from the study, if possible, an end of treatment visit should be conducted. See the Schedule of Activities for assessments to be collected at the time of study discontinuation and follow-up and for any further evaluations that need to be completed.

If a patient does not return for a scheduled visit, every effort should be made to contact the patient. All attempts to contact the patient and information received during contact attempts must be documented in the patient's medical record. In any circumstance, every effort should be made to document patient outcome, if possible. The investigator should inquire about the reason for withdrawal, request that the patient return all unused investigational product(s), request that the patient return for a final visit, if applicable, and follow-up with the patient regarding any unresolved AEs.

Subsequent to the follow-up period, overall survival (OS) follow-up will be conducted by telephone every 8 weeks (\pm 7 days) until end of the entire study (2 years after last patient first treatment). If the patient is seen in the clinic during the window of time that a scheduled telephone call is to be made to collect survival data, then the clinic visit may replace the survival telephone call.

If the patient refuses further visits, the patient should continue to be followed for survival (if survival is a secondary endpoint) unless the patient withdraws consent for disclosure of future information or for further contact. In this case, no further study-specific evaluations should be performed and no additional data should be collected. The sponsor may retain and continue to use any data collected before such withdrawal of consent.

7. ASSESSMENTS

Every effort should be made to ensure that the protocol-required tests and procedures are completed as described. However, it is anticipated that from time to time there may be circumstances outside of the control of the investigator that may make it unfeasible to perform the test. In these cases the investigator will take all steps necessary to ensure the safety and well-being of the patient. When a protocol-required test cannot be performed, the investigator will document the reason for this and any corrective and preventive actions that he or she has taken to ensure that normal processes are adhered to as soon as possible. The study team will be informed of these incidents in a timely manner.

For samples being collected and shipped, detailed collection, processing, storage, shipment instructions and contact information will be provided to the investigator site prior to initiation of the study.

7.1. Safety Assessment

Safety assessments will include collection of AEs, serious AEs (SAEs), vital signs and physical examination, electrocardiogram (ECG [12-lead]), laboratory assessments, including pregnancy tests and verification of concomitant treatments.

For alternative safety assessment logistics during public emergencies such as the COVID-19 pandemic, refer to Appendix 8.

7.1.1. Pregnancy Testing

All pregnancy tests used in this study, either urine or serum, must have a sensitivity of at least 25 mIU/mL and must be performed by a certified laboratory. For female patients of childbearing potential, 2 negative pregnancy tests are required before receiving PF-06952229 (1 negative pregnancy test at screening and 1 at the baseline visit immediately before PF-06952229 administration). Following a negative pregnancy test result at screening, appropriate contraception must be commenced and the second negative pregnancy test result will then be required at the baseline visit and within 5 days after the first day of the menstrual period (counting the first day of the menstrual period as Day 1) before the patient may receive the PF-06952229. In the absence of regular menstrual bleeding, the study candidate should have used 2 forms of contraception for at least 1 month before the second pregnancy test. Pregnancy tests will also be repeated at every treatment cycle up to Cycle 3 and every other cycle thereafter during the active treatment period, and at the end of study treatment to confirm that the patient has not become pregnant during the study. Pregnancy tests will also be done whenever 1 menstrual cycle is missed during the active treatment period and when potential pregnancy is otherwise suspected, and may be repeated if requested by institutional review boards (IRBs)/ethics committees (ECs) or if required by local regulations. In the case of a positive confirmed pregnancy, the patient will be withdrawn from administration of investigational product but may remain in the study.

7.1.2. Adverse Events

Assessment of AEs will include the type, incidence, severity (graded by the NCI CTCAE version 5.0) timing, seriousness, and relatedness.

7.1.3. Laboratory Safety Assessment

Hematology and blood chemistry will be drawn at the time points described in the Schedule of Activities and analysed at local laboratories.

Safety Laboratory Tests

Hematology	Chemistry	Coagulation	Urinalysis	Pregnancy Test
Hemoglobin	ALT	PT or INR	Urine dipstick for	For female patients
Platelets	AST	PTT	urine protein: If	of childbearing
WBC	Alk Phos		(greater than 1+),	potential, serum or
Absolute Neutrophils	Sodium		collect 24-hr and	urine
Absolute Lymphocytes	Potassium		microscopic (Reflex Testing)	
Absolute Monocytes	Magnesium		Urine dipstick for	SEROLOGY
Absolute Eosinophils	Chloride		urine blood: If positive collect a microscopic (Reflex	Hepatitis B testing**
Absolute Basophils	Total calcium			Hepatitis C virus
				Antibodies**
	Total bilirubin***		Testing)	Human immunodeficiency virus (HIV)
	BUN or Urea			Tumor markers: PSA for mCRPC
	Creatinine			
	Uric Acid			

Hematology	Chemistry	Coagulation	Urinalysis	Pregnancy Test
	Glucose (nonfasted)			
	Albumin			
	Serum Phosphorus			
	Alkaline			
	phosphatase bone			
	fraction			
	Troponin I and BNP			
	Alkaline			
	phosphatase liver			
	fraction			
	TSH at Screening			
	only			
	Testosterone at			
	Screening (mCRPC			
	patients only)			

^{**}Viral Disease Screening: Hepatitis B virus surface antigen (HBsAg), hepatitis B core antibody (anti HBc), (HbcAb), hepatitis B surface antibody (anti HBs), hepatitis C virus antibodies (HCVAb), and human immunodeficiency virus testing (HIV) to be conducted by local laboratory where required by local regulations or if warranted by patient history. ***For potential Hy's Law cases, in addition to repeating AST and ALT, laboratory tests should include albumin, creatine kinase, total bilirubin, direct and indirect bilirubin, gamma-glutamyl transferase, prothrombin time (PT)/INR, alkaline phosphatase, total bile acids and acetaminophen drug and/or protein adduct levels.

